## **Objectives**

This study will investigate the effects of a structured, supervised, home-based combined exercise intervention with self-selected intensity on the chemotherapy completion rates of women with BC. We also intend to analyze the impact of this intervention on functional performance, body composition, PA levels, and quality of life. A 3-month follow-up will be performed to investigate short-term outcomes and active lifestyle sustainability post-intervention.

Hypothesis 1: Women in the intervention will have a better completion rate than those in the control group.

Hypothesis 2: Women in the intervention will present better functional performance, body composition, PA levels, and quality of life than the control group.

Hypothesis 3: In the post-intervention period, women in the intervention group will maintain a more physically active lifestyle than women in the control group.

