## **Methods**

### **Study setting**

The Home-Combo study will take place in the Algarve, and the sample will be recruited by medical referral from various public and private hospitals, and oncologic organizations across the region.

The intervention design will consider the PA/exercise preferences, perceived barriers, and facilitators of women with BC. This information will be collected before the intervention through a mixed-methods qualitative study that will include a survey and focus groups. The intervention will be conducted online to ensure the participants' safety during the chemotherapy treatment phase, as they may have compromised immunity. Also, this option was made to attenuate participants' burden caused by commuting requirements . Due to the specific timings between the first contact and study enrolment, participants will be enrolled continuously for one year. Recruitment will continue for each cohort until the number of participants per group is achieved. A scheme of the study timeline is presented in Table 1.

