### **Eligibility criteria**

Women aged  $\geq 18$  years with a BC stage I-III diagnosis, scheduled to receive neoadjuvant or adjuvant chemotherapy, and who have access to a computer will be considered eligible to participate in the study. Women already at the mid-stage of the chemotherapy treatments, with medical counterindication to perform the exercise intervention or physical assessments due to concomitant comorbidity, non-controlled health conditions or diseases, or psychological illness, currently enrolled in a structured exercise program, or women unable to complete the entire program (e.g., due to scheduled surgery or personal commitments) will be considered ineligible. Participants who get pregnant or have a worsening in their clinical condition during the intervention will be discounted from the program.

The exercise professionals who will perform the interventions and assessments must have an academic degree in Exercise Sciences and a specialization in exercise with cancer populations or receive education sessions with an exercise professional specialized in exercise for BC populations to acquire knowledge and skills to conduct exercise sessions online. Also, professionals who conduct the interventions will have to perform at least three simulated sessions among each other, supervised by a qualified peer, to guarantee consistency in the intervention application.

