### **Allocation concealment mechanism**

Participants and research team members will be unaware of group allocation during recruitment and baseline assessments. A non-interventionist research team member will fill in the measurements' results during the field tests. This team member will be the only person, besides the participant, who will know the participant's number. The participants will identify the questionnaires with their numbers.

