### **Blinding (masking)**

Participants will be told they are part of an exercise intervention without any mention of a control group. The healthcare professionals responsible for the chemotherapy prescription and administration and registering all clinical information will be blinded to the participants' groups. None of the research team members will know the number of participants, so data analysis will be performed in a blinded setting. The exercise professional conducting the assessments will be blinded to the participant's number but not to which group the participant belongs. If, at any given moment, a participant reveals her number to a research team member, all posterior data from that participant will be disregarded. If a participant decides to leave the study or must abandon it due to health complications, the team member with the number information will be informed, and all further data will be disregarded from the analysis.

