## **Data collection, management, and analysis**

### **Data collection methods**

Assessments will be conducted in standardized conditions, in a clinical setting, in a calm and comfortable environment, in small groups, and performed by a qualified exercise professional. The assessments will be conducted in the morning, starting with the body composition measurements, followed by a 15-minute pause so participants can eat (since they will be weighted while fasting), preceded by a 10-minute warm-up with general movements to mobilize big muscle groups and the physical tests, that will be performed in the following order: shoulder angular measurements, strength, mobility, and aerobic endurance. Participants will be divided into small groups to facilitate instruction and conduction of the tests. Participants will receive the accelerometers one week before

the field tests and return them on the physical assessment day. After the field measurements, all questionnaires will be delivered and answered through email (Google Forms). Summarized information regarding assessment time points and tools can be found in Table 1.

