### **Secondary outcomes**

**Functional performance.** Functional performance will be assessed at  $T_0$ ,  $T_1$ ,  $T_2$ , and  $T_3$ . The test battery will consider aerobic capacity, upper and lower body strength, grip strength, shoulder mobility, and overall mobility. Aerobic endurance will be assessed using the 6-minute walk test, a standardized field test performed indoors in a 30-meter corridor with two turning points marked every 3 meters along the course, that has been considered valid and reliable for evaluating aerobic capacity in cancer patients . In this test, participants will be asked to walk the maximum distance possible in 6 minutes on a flat and hard surface, whereas the distance walked is the outcome . The arm curl and sit-to-stand tests will be used to test the lower and upper body strength, respectively, since they are valid and reliable in these populations . Handgrip strength will be measured using the JAMAR dynamometer since it has shown reasonable validity and reliability in measuring this variable among adults  $\geq 50$  years old and used in oncologic samples . While performing the handgrip test for each hand, participants will be instructed to stand upright with feet at hip width and elbows completely stretched while applying the maximum grip continuously for more than 3 seconds, and 30 seconds

of rest will be given between measurements . Handgrip strength will be considered to the nearest 0.1 kilograms, with each participant performing 2 attempts in each hand, and a best value will be considered . The timed up-and-go test will assess participants' overall mobility. Participants will be instructed to rise from a chair, walk 2.44 meters, turn around, walk back to the chair, and sit down . Shoulder flexion and abduction angular measures will be performed on both sides using a validated and reliable goniometer to measure this variable . Upper limb flexibility will be assessed using the back scratch test .

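### Testers know each woman's arm at T1–T3, so the effort-dependent and tester-read functional tests are open to expectation bias that could partly be avoided at little cost

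*Protocol*

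**What the plan says.** Protocol, Blinding (masking): "The exercise professional conducting the assessments will be blinded to the participant's number but not to which group the participant belongs". The same section blinds the healthcare professionals who prescribe, give and record chemotherapy, and aims for a blinded data analysis. It gives no reason for leaving the assessor aware of arm.

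Protocol, Eligibility criteria, sets one qualification for both tasks: "The exercise professionals who will perform the interventions and assessments must have an academic degree in Exercise Sciences". No section says that the two tasks must fall to different people.

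Protocol, Secondary outcomes, lists the functional battery. Several tests ask for maximal effort: in the walk test, "participants will be asked to walk the maximum distance possible in 6 minutes", and in the handgrip test the woman is instructed on "applying the maximum grip continuously for more than 3 seconds". Arm curl, sit-to-stand, timed up-and-go and goniometer readings of the shoulder complete the tests at issue here. Functional performance is measured at T0, T1, T2 and T3 and belongs to Hypothesis 2: "Women in the intervention will present better functional performance, body composition, PA levels, and quality of life than the control group".

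Three further statements bear on the point:
- Allocation follows the baseline assessments (Sequence generation; Allocation concealment mechanism), so T0 is tested without knowledge of arm.
- Allocation concealment mechanism: "A non-interventionist research team member will fill in the measurements' results during the field tests".
- Delivery and measurement happen in different places. Study setting: "The intervention will be conducted online to ensure the participants' safety during the chemotherapy treatment phase". Data collection methods: "Assessments will be conducted in standardized conditions, in a clinical setting".

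**The concern.** The masking withholds the participant number from the tester and leaves the arm known. The number matters for linking data. It has no influence on how firmly a tester encourages a woman in the last minute of a walk, when the stopwatch is stopped, or how a goniometer is read. Knowledge of arm can influence all three.

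The timing adds to the problem. Baseline is blind to allocation and the later visits are not. Any tester expectation therefore enters as a between-group difference in change from baseline, which is the pattern the planned repeated-measures ANCOVA would read as an intervention effect. An analysis plan cannot repair this, because the error arises when the test is conducted. At stake is the interpretation of the functional part of Hypothesis 2. The primary outcome is not at stake.

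**Working it through.** **1. Is the tester blind to arm?** No. The blinding section says so directly, and nothing elsewhere in the protocol reverses it.

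**2. Are delivery and testing separated?** Not by any rule. The eligibility section sets a common qualification for staff who do either task. It neither states nor excludes that a woman is tested by the person who leads her sessions.

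**3. Which outcomes and visits are exposed?**

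| Outcome | Source | Exposed to the tester's knowledge of arm? |
|---|---|---|
| 6-minute walk, arm curl, sit-to-stand, handgrip, timed up-and-go | Effort under the tester's instruction | Yes, at T1–T3 |
| Shoulder goniometry | Read by the tester | Yes, at T1–T3 |
| All functional tests at T0 | Before allocation | No |
| RDI (primary) | Medical records, blinded clinical staff | No |
| Accelerometry | Device | No |
| Quality of life and activity questionnaires | Completed by the woman through email | No |

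**4. Do the existing safeguards close the gap?** The separate recorder limits biased transcription. Standardised conditions limit differences in setting. Neither fixes what the tester says during a maximal test, and no encouragement script is specified. Blinded data analysis acts after the measurement has been made.

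**5. How much could it matter?** The protocol gives no figure for such a bias, so there is none to reproduce. What follows is an illustration under assumed shifts.

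Inputs:
- Patients per arm: 82/2 = 41 and 98/2 = 49 (Sample size section); 122/2 = 61 (Abstract).
- Two-sided α = 0.05, critical value 1.96.
- No true effect, and a tester-induced shift b of 0.1, 0.2 or 0.3 SD in favour of the intervention (assumed).

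Formulas: SE = √(2/n). Rejection probability = P(Z > 1.96 − b/SE) + P(Z < −1.96 − b/SE).

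Worked case, n = 49 and b = 0.2: SE = √(2/49) = 0.202; b/SE = 0.990; P(Z > 0.970) + P(Z < −2.950) = 0.166 + 0.002 = 0.168.

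| n per arm | b = 0 | b = 0.1 | b = 0.2 | b = 0.3 |
|---|---|---|---|---|
| 41 | 5.0% | 7.4% | 14.8% | 27.4% |
| 49 | 5.0% | 7.9% | 16.8% | 31.8% |
| 61 | 5.0% | 8.6% | 19.7% | 38.1% |

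This is an unadjusted two-group normal approximation for one test at one visit, with everyone assessed. It is not the planned ANCOVA. The row for 41 per arm shows roughly what remains if the allowance for dropout in the 98 is used up.

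**The case against.** The best defence is that the protocol discloses the limitation openly, confines it to secondary outcomes and already has partial safeguards: the separate recorder, standardised conditions, an allocation-blind baseline, and participants who are not told that there is a control group. That stands as far as it goes. It lowers the weight of the point without removing it, since none of these measures governs encouragement, timing or reading.

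A reader might infer four stronger things, which the protocol does not support:

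- **That each woman is tested by her own instructor.** The eligibility section names a class of staff and sets an additional training duty for those who lead sessions, which is compatible with distinct roles. Testing by one's own instructor is possible, but it is not stated.
- **That arm is invisible at the clinic, so the unblinding is wholly needless.** This is only inferred from online delivery and clinic testing. Women are tested in small groups and may disclose their sessions.
- **That familiarity must favour the exercise arm.** Control women also have a supervised session each week, of 30 minutes against two of 60. Leniency towards women one has coached could act in either arm. Only expectation about the exercise arm has a clear direction.
- **That a positive functional result would be uninterpretable.** The size of the bias is unknown. The assumed shifts have no source in the protocol, and one common shift across six different tests is a simplification.

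**Conclusion.** The point holds as a design weakness that should be reduced. It is not an error that undermines the trial. At T1–T3 the tester knows the arm, no rule separates testing from delivery, and six functional tests depend on the tester's conduct or reading. If there were no true effect and the tester's knowledge shifted results by 0.2 SD, a nominal 5% comparison at 49 per arm would reject in about 17% of trials, a little over three times the nominal rate (16.8/5 = 3.4). Over assumed shifts of 0.1 to 0.3 SD the range is 8% to 32% at that size. These figures show how sensitive a test of this size is to a small shift; they do not estimate this trial's bias. The conclusion about RDI is untouched.

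**What to change.** Amend the Blinding (masking) section for T1–T3 as follows:

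1. Testers are not given the allocation.
2. Where the existing pool of professionals allows it without revealing arm, no one tests a woman whose sessions she or he leads. The condition matters: in a small pool, someone who leads only exercise sessions could guess that an unfamiliar woman is a control.
3. One fixed instruction and encouragement script is used for every woman and every test.
4. At the contact already planned one week before each assessment (Plans to promote retention), women are asked not to mention their sessions to the tester.
5. The tester records a guess of arm after testing, so that the success of blinding can be reported.

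If existing staff cannot be separated, keep items 3 to 5 and interpret the functional results as unblinded. Dedicated assessors who lead no sessions would be cleaner, but they could need extra staff, and the protocol foresees no funding, so this is not asked for.

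The cost is a short protocol edit, a script and some rostering, with no added visits or staff. Scheduling becomes less flexible, and blinding will remain incomplete because some women will reveal their arm.

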### **Primary outcome**

**Chemotherapy completion rates.** Chemotherapy completion rates will be assessed at  $T_0$ ,  $T_1$ , and  $T_2$ . This outcome will be reported as the mean RDI ( $\text{mg} \cdot \text{m}^{-2} / \text{wk}^{-1}$ ), which corresponds to a fraction of the planned chemotherapy dose intensity, by dividing the dose of chemotherapy per square meter (of surface area where the drug is related) in each cycle by the number of weeks in a cycle . Information regarding the planned chemotherapy treatment and the effectively received treatment (i.e., dose, type, and duration) will be acquired from medical records after signing the informed consent . A successful chemotherapy completion rate will be considered if the RDI is  $\geq 85\%$  of the planned treatment, as an RDI below this cut-off is associated with a worse disease prognosis and lower treatment efficacy . Calculations to compare the actual chemotherapy dose intensity received and the initially planned dose intensity will be calculated as total milligrams of chemotherapy divided by the product of the body surface (in square meters) and total weeks of treatment . The RDI results from the actual dose intensity received are divided by the planned dose intensity .

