### **Statistical methods**

All data will be analyzed using IBM SPSS (version 29.0). Factorial ANCOVAs with repeated measures will be used for the primary and secondary outcomes, adjusted for potential covariates (e.g., concomitant treatments, BC diagnosis, neo-adjuvant/adjuvant chemotherapy). Independent sample T-tests will be used to compare results between groups at each time point, considering chemotherapy completers versus non-completers . A Fisher's exact test will compare the proportion of participants who needed chemotherapy adjustments from those who did not . The intention-to-treat analysis will be conducted to ensure that all participants are included in the overall assessment, considering their compliance with the study protocol. The Last Observation

Carried Forward method will be used to input missing data values. A per-protocol analysis will also be conducted without participants who failed to complete at least 50% of the training sessions. Normality plots and Kolmogorov-Smirnov tests will be performed to test the normality of outcome variables. If normality is not satisfied, non-parametric tests will be applied (e.g., Krustal-Wallis). Mediators of change (i.e., mechanisms by which RDI) will be explored using structural equation modeling (AMOS 18.0) and multiple mediation analysis (PROCESS macro for SPSS). Putative candidates will include treatment (e.g., dose planned vs. given dose, planned cycles minimum/maximum, treatment interruption ratios, response to treatment, percentage of participants who needed dose adjustments, and the mean value of dose adjustment), and physiological (e.g., body composition, functional performance, handgrip strength, PA levels) variables. Mediation occurs when a causal effect of an independent variable occurs on a dependent variable, partly or entirely explained by a mediator. Indirect effects testing will be performed using Preacher and Hayes' procedures.

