## **Harms**

All participants will have their adverse events monitored throughout the study, whether directly related to the intervention or not (if applicable). This monitoring will be done through self-reporting at the start of each session, registered for analysis and report purposes, or by their primary care physicians. Participants will be advised to contact the clinical team if they have difficulties.

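### Disregarding all data after a participant reveals her number is a post-randomisation exclusion that conflicts with the protocol's intention-to-treat and adverse-event commitments and does not restore blinding

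*Protocol*

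**What the plan says.** The Blinding (masking) section of the protocol sets the rule: "If, at any given moment, a participant reveals her number to a research team member, all posterior data from that participant will be disregarded". No type of data is exempted.

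Four other statements bear on it.

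- **Who is blinded.** The same section says "The healthcare professionals responsible for the chemotherapy prescription and administration and registering all clinical information will be blinded to the participants' groups". Of the physical assessments it says "The exercise professional conducting the assessments will be blinded to the participant's number but not to which group the participant belongs". It also explains why numbers are kept secret: team members who do not know them can analyse the data blind.
- **Primary outcome.** "Information regarding the planned chemotherapy treatment and the effectively received treatment" is the raw material for RDI, and it "will be acquired from medical records after signing the informed consent".
- **Analysis.** Under Statistical methods, "The intention-to-treat analysis will be conducted to ensure that all participants are included in the overall assessment". The same section fills missing values by last observation carried forward (LOCF).
- **Safety.** Under Harms, "All participants will have their adverse events monitored throughout the study, whether directly related to the intervention or not", and the events are recorded so that they can be analysed and reported. The Data monitoring section provides for no monitoring committee.

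**The concern.** A woman who tells a team member her number has done nothing that changes her chemotherapy, her adverse events or the arm she was randomised to. Yet from that moment her outcomes no longer count. An event after randomisation, unrelated to the validity of the record-based data, decides which data enter the comparison.

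Two things are at stake. First, the RDI comparison would rest partly on imputed values although the true values sit in the hospital record. Second, adverse events after the disclosure would be left out of the safety report, in a trial where that report is the main safety evidence described.

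**Working it through.** The rule rests on no figure in the protocol, so the main check sets the sections side by side. The arithmetic in steps 4 and 5 is illustrative.

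**1. Against intention to treat.** Statistical methods wants every participant in the assessment. The disclosure rule removes a randomised woman's later outcomes. The intention-to-treat sentence ends with a loose reference to compliance. However, a separate per-protocol analysis, defined by attendance, is already planned, so that ending does not license a further exclusion.

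**2. Against Harms.** Events cannot be recorded for analysis in all participants throughout the study and also be disregarded in some of them from a given date.

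**3. Effect on RDI.** RDI is assessed at T0 (1-2 weeks after chemotherapy starts), T1 (mid-treatment) and T2 (3-4 weeks after chemotherapy ends). If disregarded values are treated as missing and LOCF is applied:

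| Disclosure falls | RDI values set aside | Value used for T2 |
|---|---|---|
| between T0 and T1 | T1 and T2 | T0 |
| between T1 and T2 | T2 | T1 |

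At T0 there has been little time for delays or dose reductions, so a carried-forward T0 value probably overstates completion. That direction is a judgement; the protocol gives no RDI data. The protocol also does not say outright that disregarded values go through LOCF. The alternative, dropping the woman, conflicts with intention to treat even more plainly.

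**4. How many women, and in which arm.** Inputs from the protocol: two 60-minute sessions a week in the exercise arm, one 30-minute session a week in control, about 6 months of intervention, 1:1 allocation, and 98 participants in the Sample size section (49 per arm). Assumptions: 24 weeks, full attendance, and an equal chance p of disclosure per session. The share with at least one disclosure is 1 − (1 − p)^n, with n = 48 against 24.

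| p per session | Exercise | Control | Women of 49 | Ratio |
|---|---|---|---|---|
| 0.05% | 2.4% | 1.2% | 1.2 v 0.6 | 1.99 |
| 0.1% | 4.7% | 2.4% | 2.3 v 1.2 | 1.98 |
| 0.2% | 9.2% | 4.7% | 4.5 v 2.3 | 1.95 |
| 0.5% | 21.4% | 11.3% | 10.5 v 5.6 | 1.89 |

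With 22 to 26 weeks the ratio stays between 1.88 and 1.99. If risk followed contact time, it could approach 120 / 30 = 4. If disclosures happened only at the assessments, which are scheduled alike in both arms, it would be 1.

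**5. Power.** The protocol's initial 82 is reproduced with f = 0.25, two groups, four measurements, correlation 0.5 and alpha 0.05 (power 0.808). Of these, the protocol states only the two groups, the alpha and a moderate effect size; the rest is assumed. If affected women were left out altogether, power would be 0.798 with 2 lost, 0.782 with 5 and 0.754 with 10. Power is the smaller issue; bias is the larger.

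**The case against.** The strongest defence is that the rule has a purpose. The number is the key between a known person and her row of data. Exercise staff know who is in which arm, and the Implementation section has the numbers in each group emailed to all participants. A number attached to a person therefore can unblind an analyst. This stands, and it would be wrong to say that the number protects nothing. But the rule does not repair the breach: the woman's earlier data, under the same number, stay in the analysis, so the analyst can still identify her row and her arm. Nor does the breach taint later RDI, which others record. For the physical assessor, who already knows the group, the number adds nothing.

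A reader might also infer three stronger points that the protocol does not support.

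- **That reporting a harm triggers the rule.** Nothing shows numbers being used in sessions or harm reports. Participants are told to keep them private, attendance lists are converted to numbers afterwards by a non-interventionist member, and women in difficulty are directed to the clinical team.
- **That the exercise arm will be hit harder.** This needs a non-zero per-session risk that is similar in both arms. The protocol gives no rate.
- **That data are deleted.** The word used is disregarded. Collection continues; the conflict concerns use in analysis and reporting.

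It is also fair to say that disclosure is avoidable and may be rare. The exclusions tied to health and adherence elsewhere in the protocol may matter more for bias. That lowers the urgency but does not make this rule sound.

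**Conclusion.** The rule is wrong as written and should be fixed. It contradicts the protocol's own intention-to-treat and adverse-event statements, sets aside a primary outcome that remains retrievable and was recorded by group-blinded staff, and fails to restore the blinding it is meant to protect. None of this depends on how often disclosures occur or in which arm.

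The size cannot be fixed from the protocol. The loss may be larger in the exercise arm, with a ratio anywhere from 1 to about 4. The counts in the table rest on assumed disclosure rates and only show the scale. The upward bias in RDI rests on reading the disclosure rule together with LOCF and on dose problems building up over the course.

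**What to change.** Replace the sentence in Blinding (masking) with:

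> If a participant reveals her number, the disclosure is logged as a protocol deviation with its date and a new number is issued; all her data, including adverse events and RDI, are kept and analysed in her randomised arm.

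Moving her earlier rows to the new number would also break the link that the disclosure created, which the present rule does not do. If wanted, add a sensitivity analysis that leaves out assessor-rated field tests obtained after a disclosure.

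The cost is one sentence, a deviation log and a protocol amendment, with no extra visits. The small downside is that assessor-rated values obtained after a disclosure stay in the main analysis.

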### **Plans to promote retention**

The conducting exercise professional will control participants' adherence to the exercise program through a presence registry collected by the research team member with access to the list of participants' numbers. After the session, the non-interventionist research team member will pass the presence list to the respective numbers of the participants for program adherence analysis. If a participant fails to attend a session, contact will be made to ensure the participant's welfare and motivate them to participate

in the next session. The data analysis will not consider participants who fail to attend 50% or more sessions. Positive feedback will be given to the participants during the sessions, as positive feedback is proven to enhance feelings of competence, enjoyment, and interest in the activity . Additionally, participants will be encouraged to keep an activity diary where they may register all activities performed autonomously. Participants will be contacted one week before the assessment to confirm their availability and presence. Data from participants who fail to perform the assessments during the intervention period will be excluded from data analysis. After the intervention, participants will be contacted monthly to check their well-being and keep their interest and motivation in engaging in the follow-up assessment.

\*\*\* Table 2\*\*\*

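### The rule that discards all data after a woman leaves the study makes no exception for RDI, so a primary outcome still available in the medical records may be lost

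*Protocol*

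**What the plan says.** Four parts of the Protocol bear on this.

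- **Blinding (masking).** The rule covers a woman who quits the study by choice and, equally, one who "must abandon it due to health complications, the team member with the number information will be informed, and all further data will be disregarded". It names no outcome that is exempt. The same section says that the clinical staff who prescribe, give and register chemotherapy are blinded to group.
- **Primary outcome.** "This outcome will be reported as the mean RDI", assessed at T0, T1 and T2. "Information regarding the planned chemotherapy treatment and the effectively received treatment (i.e., dose, type, and duration) will be acquired from medical records". RDI compares received with planned dose intensity, using total dose and total weeks of treatment.
- **Plans to promote retention.** "Data from participants who fail to perform the assessments during the intervention period will be excluded from data analysis". Again RDI is not exempted.
- **Statistical methods.** "The intention-to-treat analysis will be conducted to ensure that all participants are included in the overall assessment". For gaps, the Last Observation "Carried Forward method will be used to input missing data values". A per-protocol analysis without women who attended too few sessions is planned as well.

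**The concern.** The two rules suit outcomes that need the woman to be present, such as walk tests, bioimpedance, accelerometry and questionnaires. RDI needs none of these. Once a woman has consented to abstraction, her planned and received chemotherapy stay in her records whether or not she attends anything further. Discarding her later data therefore creates a missing primary outcome where none need exist.

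The loss is unlikely to be random. One trigger for the rule is a health complication, which is also a plausible cause of delayed or reduced doses. The women whose T2 RDI is discarded may thus be those with the lowest RDI. At stake is whether the primary comparison reflects what all randomised women received, or a mixture of final values and early values from those who left.

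**Working it through.** **1. What is lost and what replaces it.** T0 falls 1-2 weeks after chemotherapy starts, T1 at planned mid-course, and T2 3-4 weeks after it ends (Outcomes). Final RDI needs the whole course. A woman who exits after T1 has her T1 value carried forward. One who exits before T1 has her T0 value, taken before most delays or reductions can occur. If the missed-assessment rule is applied instead, she is removed. Because the staff who register chemotherapy are blinded to group, blinding gives no reason to discard RDI after exit.

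**2. The plan's own dropout allowance.** Sample size starts from 82 and allows for 20% dropout: 82 x 1.2 = 98.4, i.e. 98. That leaves room for 98 - 82 = 16 exits. Arms are 98/2 = 49, or 122/2 = 61 with the Abstract's recruitment goal.

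**3. One woman's RDI (assumed course).** Assume 8 three-week cycles (24 weeks), 2 weeks of delay, a 25% reduction in every remaining cycle, and 100% at the last recorded value.

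- Exit after T1 (cycle 4): dose (4 + 4 x 0.75)/8 = 0.875; RDI = 0.875 x 24/26 = 80.8%. Gap to the carried value: 100 - 80.8 = 19.2 points. She also moves from below to above the Protocol's 85% success cut-off.
- Exit before T1 (reduction in cycles 3-8): (2 + 6 x 0.75)/8 = 0.8125; x 24/26 = 75.0%. Gap: 25 points.

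**4. Effect on one arm's T2 mean, per such woman.**

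| Route | 49 per arm | 61 per arm |
|---|---|---|
| T1 carried forward | 19.2/49 = 0.39 | 19.2/61 = 0.32 |
| T0 carried forward | 25/49 = 0.51 | 25/61 = 0.41 |
| Excluded, others averaging 95% | (95 - 80.8)/49 = 0.29 | 14.2/61 = 0.23 |

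**5. Effect on the between-arm difference at T2.** Bias (exercise minus control) = gap x (kE - kC)/49, where kE and kC are the numbers of such exits. Suppose 8 of the 16 exits fit the after-T1 profile.

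- Split 4/4: each arm is overstated by 19.2 x 4/49 = 1.6 points; the bias in the difference is 0.
- Split 5/3: 19.2 x 2/49 = 0.8 points toward exercise. Split 3/5: 0.8 points against it.
- If reductions had begun by T1 and the gap were only 5 points, the 5/3 split gives 5 x 2/49 = 0.2 points.

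**6. Equal exit proportions are not the same as equal numbers.** Let shares pE and pC of women be at 80.8% and the rest at 100%, and let fractions fE and fC of the low-RDI women exit. The observed difference is 19.2 x [pC(1 - fC) - pE(1 - fE)].

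- pE = 0.10, pC = 0.20, no exits: 1.9 points (the true difference). Half exiting in both arms: 1.0 point, so a real effect is halved.
- pE = pC = 0.20 (no effect): fE = 0.50, fC = 0.25 gives +1.0 point; reversed, -1.0 point.

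**7. A second set of assumptions.** With total exits of 25% and 15% and a gap of 5 to 20 points, the shift is (0.25 - 0.15) x gap = 0.5 to 2 points. With 20% in each arm it is 0. With 15% and 25% the sign reverses.

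**8. Which contrast.** These are shifts in the T2 mean. In a group effect averaged equally over T0, T1 and T2, an error at T2 alone counts for one third: 0.78/3 = 0.26 points for the 5/3 split.

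**The case against.** The strongest reply is that the text can be read coherently. Data stop at exit, the last value is carried forward, and every woman stays in the analysis. The intention-to-treat sentence is paired with carry-forward, and its closing clause refers to compliance with the protocol. This stands in part. A reader might infer that the plan flatly breaks its intention-to-treat promise or drops all leavers. The documents do not support that: carry-forward can keep a leaver in the set, and what is then lost is her observed T2 value. Outright removal arises only through the missed-assessment rule.

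Second, a reader might infer that every woman who stops the sessions loses her later RDI. The wording does not go that far. Eligibility criteria and the section on discontinuing interventions speak of the program or the intervention, whereas the discard rule speaks of the study. The per-protocol analysis implies that poor attenders remain in the main one. For voluntary leavers, ending data use may simply respect a withdrawal of consent. The firm case is a woman who must abandon the study for health reasons without withdrawing consent to use of her records.

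Third, it is tempting to say that the bias favours exercise, because the scheduled load is 2 x 60 = 120 minutes a week against 30. But load and speed are self-selected, rest is allowed at will, and the program may be tailored, so more health exits under exercise cannot be presumed.

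Fourth, the same section says that once a woman reveals her number "all posterior data from that participant will be disregarded". That also covers RDI, but it is a separate blinding safeguard. Nothing in the Protocol indicates how often it would apply, so no impact is claimed.

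**Conclusion.** The point holds as a stated rule that gives a worse result than the available data allow. RDI after study exit is normally obtainable from records kept by blinded staff. The Protocol nevertheless discards it, and then either substitutes an earlier, probably higher value or excludes the woman. This undermines the intention-to-treat analysis of the primary outcome.

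The size and direction of bias in the between-arm difference are unknown. The illustrations give about 0 with equal numbers of affected exits and roughly 1 point in the T2 mean with moderate imbalance, in either direction. They rest on an assumed schedule and on a profile at the high end: a perfect RDI carried forward, then a 25% reduction in every remaining cycle plus 2 weeks of delay. Women already reduced by T1 would show a smaller gap, and an effect averaged over time points would dilute it further. Larger biases can be constructed by supposing that every planned dropout fits this profile and that exits are very unevenly split, but nothing in the Protocol supports that. Confidence is moderate, mainly because the boundary between stopping the program and leaving the study is not sharply drawn.

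**What to change.** Three additions to the wording of the Protocol:

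1. **Blinding (masking).** Keep the existing sentence, which also informs the holder of the participant numbers and governs the other outcomes, and add: *This does not apply to the primary outcome: unless the participant withdraws consent to use of her medical records, planned and received chemotherapy are taken from the records up to T2 and her RDI is analysed in her allocated arm.*
2. **Plans to promote retention.** State that the exclusion for missed assessments does not apply to RDI in the intention-to-treat analysis.
3. **Statistical methods.** State that last observation carried forward is not used for RDI when the records give the value.

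The cost is small. No visits are added, because record abstraction is already planned, and the sample size is unchanged. Abstraction continues after exit. The consent form is not among the documents, so the team should check that it covers this and add a sentence if it does not. The change goes to the ethics committees under Protocol amendments.
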